#### 10.2.2 Subgroup Analyses for Secondary Efficacy Endpoints

Subgroup analyses by the variables defined in Sections 8.2.7.1, 8.2.7.2, 8.2.7.3, 8.2.7.4, and 8.2.7.5 will be performed using the ITT Analysis Set as described in Section 10.2.1 for the following secondary endpoints:

- All-cause mortality;
- Incidence of tracheal intubation from randomization to Day 28;
- Clinical status assessed on an 8-point NIAID ordinal scale.

The logistic regressions will not include the factor for the respective subgroup analysis as independent variable (if applicable), but they will include the other covariates as specified for the primary analysis.

Forest-plots will be provided for the treatment comparison and 95% CIs for each subgroup level.

#### 10.2.3 CCI

CCI

CCI

CCI

### 10.3 Multiple Comparisons and Multiplicity

There will be 1 confirmatory test. All other statistical tests are meant to be descriptive. The sample size re-estimation at the interim analysis should not have an impact on the Type I error rate according to [Chen et al \[2004\]](#) and [Mehta and Pocock \[2011\]](#).

### 10.4 Missing Data and Imputation

For the primary efficacy analysis using the ITT Analysis Set, subjects with less than 28 days of the Treatment Period and without documented intubation or death will be considered as not having progressed to tracheal intubation or death prior to tracheal intubation in the primary analysis.

Sensitivity analyses as described in Section 10.1.3.1 will be performed to assess the impact of missing data on the primary efficacy results.

### 10.5 Treatment Compliance

Randomized subjects will receive 1 dose of IP administered by study personnel at the hospital. It is not expected that there will be any compliance issues.

## 11 Safety Analyses

The safety analyses will be based on the Safety Analysis Set as defined in Section 6 and on the treatment which the subject received.

### 11.1 Extent of Exposure

Subjects will receive 1 dose of IP. Duration of exposure is not relevant in this study. Duration of follow-up is of interest as this has an impact on the reporting of efficacy events and AEs.

Duration of follow-up will be descriptively summarized by treatment and total. The duration of follow-up is defined as:

$$\text{Subject's duration of follow-up (days)} = \text{EOS date} - \text{date of randomization} + 1,$$

where EOS date is either Day 28 or withdrawal date for subjects who discontinued.

A summary table will be provided with descriptive statistics as specified in Section 7 for:

- Duration of follow-up [days] per subject;
- Volume [mL] received per subject.

A by-subject listing will be provided based on the Safety Analysis Set including:

- Infusion date, start and end time, and duration (if start and end time is available);
- Volume administered [mL], location of infusion;
- Dose modified with reason.

## 11.2 Adverse Events

AEs will be coded using MedDRA. The version will be presented in the tables and listings. Treatment-emergent AEs (TEAEs), defined as AEs starting on or after the date (and time) of the administration of IP will be summarized. All AEs will be listed regardless of their start date.

Where AE start dates and/or times are missing or partially missing, AEs will be assumed to be treatment-emergent, except the partial dates and/or times or the AE end date and/or time indicate that the AE started before the first administration of IP:

Missing Elements of AE Start	Rule	Assignment
any	AE end date and time < IP start date and time	non-TEAE
any	AE end date and time $\geq$ IP start date and time	TEAE
otherwise		
all		TEAE
day and month	AE start year $\geq$ IP start year	TEAE
	AE start year < IP start year	non-TEAE
day	AE start month / year $\geq$ IP start month / year	TEAE
	AE start month / year < IP start month / year	non-TEAE
time	AE start date $\geq$ IP start date	TEAE
	AE start date < IP start date	non-TEAE

If AE start dates or end dates are missing or partially missing for an AE, duration will not be calculated. If for a TEAE the relationship to study treatment is missing the relationship to study treatment will be assumed to be “Yes” following a worst-case approach. No imputation

will be done in case of missing study treatment relationship for non-treatment emergent AEs. No other imputations for missing AE information will be done.

TEAEs occurring within 24 hours of IP administration will be defined as TEAEs with start date and time during IP administration or until 24 hours after the end of IP administration. AEs with missing start time will be assigned following the worst-case principle, i.e. when the start date of the TEAE is less or equal than the end date of the infusion + 1, the TEAE will be considered to having occurred within 24 hours after IP administration.

AEs fulfilling the definition of an AESI for this study will be ticked in the AE CRF. It will be ensured during data cleaning that the AESI recording on the AE CRF matches the AESI definition obtained by Standardized MedDRA Queries (SMQ):

- Hypersensitivity events corresponding to Hypersensitivity (SMQ) (broad);
- Anaphylactic reactions corresponding to Anaphylactic reaction (SMQ) (broad);
- Thromboembolic events (TEE) corresponding to Embolic and thrombotic events (SMQ);
- Bleeding events corresponding to Haemorrhages (SMQ).

All summary tables will be presented by actual treatment and total.

An overview summary table of TEAEs, including the number and percentage of subjects and the number of events will be provided for the following entries:

- Any TEAE;
- TEAEs related to study treatment;
- TEAEs occurring within 24 hours of IP administration;
- TEAEs leading to study discontinuation;
- TEAEs leading to dose modifications;
- Treatment-emergent AESIs;
- Treatment-emergent AESIs related to study treatment;
- Any serious TEAEs;
- Serious TEAEs related to study treatment;
- Serious TEAEs occurring within 24 hours of IP administration;
- Fatal TEAEs;
- Fatal TEAEs related to study treatment;
- TEAEs by intensity.

The following tables will be generated for TEAEs, including the number and percentages of subjects and the number of events. The tables will always be sorted by System Organ Class (for tables including System Organ Class) and Preferred Term within System Organ Class or Preferred Term alone (for the table not including System Organ Class). The order of the System Organ Class blocks or the order of the Preferred Terms alone or within System Organ Class block (if applicable) will be by descending frequency of number of subjects using the total column (in case of equal number of subjects sorting will be by descending frequency of number of events, in case of equal number of events sorting will be alphabetically).

- TEAEs by System Organ Class and Preferred Term;
- TEAEs by Preferred Term;
- TEAEs by System Organ Class, Preferred Term, and intensity;
- Related TEAEs by System Organ Class and Preferred Term;
- TEAEs occurring within 24 hours of IP administration by System Organ Class and Preferred Term;
- Fatal TEAEs by System Organ Class and Preferred Term;
- Treatment-emergent AESIs by System Organ Class and Preferred Term;
- Serious TEAEs by System Organ Class and Preferred Term.

The following by-subject listings based on the ITT Analysis Set will be provided including the information from the CRF:

- Deaths;
- Non-TEAEs;
- TEAEs;
- SAEs;
- AEs leading to study discontinuation;
- AESIs: hypersensitivity including anaphylactic reactions;
- AESIs: TEEs;
- AESIs bleeding events.

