10.1 Definitions

10.1.1 Adverse Event

As per ICH E2A (Clinical Safety Data Management: Definitions and Standards for Expedited Reporting), an AE is any untoward medical occurrence in a patient or clinical investigation subject administered a pharmaceutical product and which does not necessarily have a causal relationship with this treatment. An AE can, therefore, be any unfavorable and unintended sign (including an abnormal, clinically significant laboratory finding), symptom, or disease temporally associated with the use of a medicinal (investigational) product, whether or not considered related to the medicinal (investigational) product.

The period of observation for AEs extends from the time that informed consent is obtained until the EOS Visit (see [Section 10.4](#) for further details).

Adverse events may include:

- Exacerbation (ie, an increase in the frequency or severity) of a pre-existing condition. Illness present before study entry should be recorded in the medical history section of the eCRF and only be reported as an AE if there is an increase in the frequency or severity of the condition during the study.
- A clinical event occurring after consent but before IP administration.
- Intercurrent illnesses with an onset after administration of IP.

Adverse events do not include:

- Events identified at Screening that meet exclusion criteria.
- Medical or surgical procedures (the condition that leads to the procedure is the AE).
- Situations where an untoward medical occurrence has not taken place. For example:
 - Planned hospitalizations due to pre-existing conditions, which have not worsened.
 - Hospitalizations that occur for procedures not due to an AE (eg, cosmetic surgery).
 - Hospitalizations for a diagnostic procedure where the hospital stay is less than 24 hours in duration or for normal management procedures (eg, chemotherapy).

- Overdose of IP or any concomitant therapy that does not result in any adverse signs or symptoms.

For laboratory safety parameters, any instances of absolute values being outside the reference range or changes at any visit after study start that are considered by the investigator as clinically significant must be recorded in the eCRF as AEs. In addition, at the investigator's discretion, any changes or trends over time in laboratory parameters can be recorded in the eCRF as AEs if such changes or trends are considered to be clinically relevant, even if the absolute values are within the reference range.

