11.5 Analysis of Safety

Adverse events will be coded using the Medical Dictionary for Regulatory Activities (MedDRA) version 21.1 (or higher). A treatment-emergent adverse event (TEAE) is defined as an AE reported at or after the start of the first administration of study treatment. Only TEAEs will be summarized.

An overview summary of TEAEs, including counts and percentages of subjects with any TEAE; TEAEs related to study treatment; TEAEs leading to permanent discontinuation of study treatment; TEAE leading to dose modifications; serious TEAEs; serious TEAEs related to study treatment; fatal TEAEs; fatal TEAEs related to study treatment, TEAEs by severity, and TEAEs of special interest will be produced.

TEAEs will be summarized by system organ class and preferred term. TEAEs will also be summarized by causality and severity. All TEAE summaries will be provided for each treatment and overall.

Number and percentage of subjects with plasma anti-CSL312 antibodies will be summarized by treatment group and overall.

Laboratory evaluations (hematology, biochemistry, and urinalysis) will be summarized descriptively by treatment group.

Vital sign findings and respiratory parameters will be listed by subject and time point. The values and change from Baseline at each visit will be descriptively summarized by treatment group.

The Safety Analysis Set will be used for all safety analyses.

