## 5 Changes from the Protocol Planned Analyses

There are no changes to the analyses planned as specified in the study protocol.

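### Protocol and SAP define a treatment-emergent AE differently (by report versus by onset), and neither says how to count an AE that begins between consent and dosing and worsens afterwards

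*SAP*

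**What the plan says.** In Protocol 11.5 a TEAE is "defined as an AE reported at or after the start of the first administration of study treatment", and the same section adds "Only TEAEs will be summarized". SAP 11.2 speaks of TEAEs, "defined as AEs starting on or after the date (and time) of the administration of IP will be summarized", followed by "All AEs will be listed regardless of their start date". SAP 5 states: "There are no changes to the analyses planned as specified in the study protocol".

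AEs are collected from informed consent (Protocol 10.1.1 and 10.4). Protocol 10.1.1 names among possible AEs "A clinical event occurring after consent but before IP administration". Serious events in that interval go into the eCRF like any other SAE (Protocol 10.6.2). Screening lasts up to 2 days (Protocol 3.2).

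On worsening, Protocol 10.1.1 deals with illness present before study entry: it should "only be reported as an AE if there is an increase in the frequency or severity of the condition during the study". No comparable instruction covers an AE that begins after consent and progresses after dosing, and neither TEAE definition mentions an increase in severity or seriousness.

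**The concern.** There are two separate defects.

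1. **The definitions do not match.** One turns on reporting and the other on onset, yet the SAP says that it changes nothing. An event that starts before dosing and is first reported afterwards is treatment-emergent in one document and not in the other.
2. **Worsening is not addressed.** An AE can begin in the hours before dosing and become severe, serious or fatal under treatment. If the site keeps it as one record with its true start date, the SAP classes it as not treatment-emergent, and every AE summary table in SAP 11.2 is restricted to TEAEs.

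What is at stake is the comparative safety display: the TEAE, serious TEAE, fatal TEAE and AESI tables. The fatal TEAE and AESI tables may rest on few events, so one subject more or less is visible there.

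**Working it through.** The plan states no figure to reproduce, so the check is to apply each definition literally to constructed timelines.

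**Rules applied**
- Protocol 11.5: TEAE if first reported at or after the start of IP.
- SAP 11.2, complete start date and time: TEAE if onset is at or after IP.
- SAP 11.2, incomplete start: under the first two rows of the missing-start table, TEAE if the AE ends at or after the start of IP.

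**Timelines** (hours relative to the start of IP; constructed for illustration)

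| Case | Onset | First report | End | Protocol 11.5 | SAP 11.2, full start | SAP 11.2, incomplete start |
|---|---|---|---|---|---|---|
| 1. Begins, reported and resolves before dosing | -12 | -10 | -2 | No | No | No |
| 2. Begins before, first reported after | -12 | +6 | +48 | **Yes** | **No** | Yes |
| 3. Begins and reported before, worsens or turns fatal after, one record | -12 | -10 | +72 | No | No | Yes |
| 4. Illness present before entry, worsening entered as a new AE dated at the worsening | +24 | +25 | +72 | Yes | Yes | Yes |
| 5. Begins after dosing | +5 | +6 | +9 | Yes | Yes | Yes |

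**What follows**
- With complete dates, the definitions differ only in case 2.
- Case 3 is the worsening gap, and both documents share it. If the worsening event was first reported after dosing, it falls under case 2: the protocol keeps it and the SAP omits it.
- In cases 2 and 3 the SAP's answer depends on how complete the start date is. A full pre-dose start removes the event; an incomplete one retains it.

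**Fatal events.** SAP 10.1 and 10.2 identify a death from an SAE record with a fatal outcome and take that record's end date as the date of death. Suppose case 3 ends in death at +72 hours. Its end date falls between randomization and Day 28, so it adds 1 to all-cause mortality, and it also counts in the primary endpoint if the subject had not been intubated. Its start date is before dosing, so it adds 0 to fatal TEAEs. The two counts then differ without a stated reason.

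**Size per subject.** With 62 per arm (Protocol 11.1), one reclassified subject moves an arm's incidence by 1/62 = 0.016, or 1.6 percentage points. If the sample were raised to 124 per arm (SAP 4.4), the shift would be 1/124 = 0.8 points.

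**Number of subjects affected.** The documents give no AE rates, reporting delays or share of AEs that worsen, so this cannot be computed.

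**The case against.** The strongest reply is that *reported* in the protocol is loose drafting for onset, that the SAP made it precise, and that few events are touched. Several parts of this stand.

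- **The window is short.** Screening can take place on Day 1 (Protocol 3), and when eligibility is assessed at admission, randomization must follow within 24 hours (Protocol 6.1).
- **COVID-19 progression is mostly captured.** The disease is present before entry, so its worsening is an AE in its own right under Protocol 10.1.1 and would normally carry a post-dose start date.
- **Omitted events are not lost.** They remain in the listings, and SAP 11.2 has separate listings for deaths, SAEs and non-TEAEs. Deaths from randomization to Day 28 are compared between arms whatever their TEAE status.
- **Sites may already open a new record at worsening.** That depends on CRF completion instructions, which are not among the documents.
- **No safety hypothesis is tested.** SAP 10.3 plans a single confirmatory test.

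A reader might go further and infer that bleeds or clots worsening under CSL312 could be hidden from the comparison. The documents give little support for that: active bleeding and recent thrombotic events are exclusion criteria (Protocol 6.3), and events found at Screening that meet an exclusion criterion are not AEs (Protocol 10.1.1).

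The reply does not remove the mismatch. If *reported* was meant as onset, the protocol text still needs correcting. Version lag is an unlikely explanation: the SAP is based on Amendment 2, but the Amendment 3 log names only contraception duration and thermometry. The missing worsening rule is also untouched by the reply.

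**Conclusion.** The point holds as a wording defect with a limited reach. The definitions conflict for AEs that begin between consent and dosing and are first reported after dosing. Both documents also lack a worsening criterion, so a fully dated AE from that window that worsens after dosing and stays on one record is absent from the SAP's TEAE tables. Fatal TEAEs and all-cause mortality could therefore disagree. The number affected is probably small, at about 1.6 points of incidence per subject with 62 per arm. This rests on reading both definitions literally and on the worsening not being entered as a new AE.

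Two stronger readings are not supported.

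- A reader might divide 2 days of Screening by 30 days of participation and infer that 2/30 = 6.7% of AEs change status. That assumes a full 2-day Screening for everyone and a constant AE rate. Even then it gives the share that begins before dosing, not the share that the two definitions classify differently. An AE that both begins and is reported before dosing is not a TEAE under either.
- A reader might infer that the SAP alone loses worsening events. The protocol wording loses them too when they were reported before dosing.

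**What to change.** 1. Use one onset-based definition in Protocol 11.5 and SAP 11.2, replacing *reported* with onset in the protocol.
2. Count as a TEAE any AE with onset before IP that increases in severity, becomes serious or becomes fatal at or after the start of IP.
3. Implement step 2 by one mechanism only:
   - a clause in the definition, with the event kept as one record; or
   - an eCRF instruction to open a new AE record dated at the worsening, which the onset rule then captures.

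   Using both could turn one worsening into two TEAEs, because the SAP tables report numbers of events as well as subjects.
4. List the change in SAP 5.

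The cost is wording in two sections, the entry in SAP 5 and, if the second mechanism is chosen, one eCRF completion instruction. The primary analysis is unaffected. The small downside is that some natural disease worsening will count as treatment-emergent, in both arms.

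### For AEs with an incomplete start date or time, the SAP 11.2 table lets a post-dose end date override a known pre-dose start, contrary to the SAP's own onset rule

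*SAP*

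**What the plan says.** SAP 11.2 defines treatment-emergent events by onset: "defined as AEs starting on or after the date (and time) of the administration of IP will be summarized". Protocol 11.5 is worded more loosely; there a TEAE "is defined as an AE reported at or after the start of the first administration of study treatment". Neither definition refers to when the event ended.

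For incomplete start dates or times, SAP 11.2 sets a default with an exemption: "AEs will be assumed to be treatment-emergent, except the partial dates and/or times or the AE end date and/or time indicate" that the event began before the first dose. Evidence from the partial start or from the end is enough.

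The table that follows has two blocks:

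- **Any start element missing.** "AE end date and time < IP start date and time" gives non-TEAE; "AE end date and time $\geq$ IP start date and time" gives TEAE.
- **Otherwise.** The known part of the start is compared with dosing. For example, "AE start month / year < IP start month / year" (day missing) and "AE start date < IP start date" (time missing) both give non-TEAE.

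Pre-dose events do enter the database. Protocol 10.1.1 counts as an AE "A clinical event occurring after consent but before IP administration".

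**The concern.** The first block covers every event with a usable end, so the second block operates only when the end is unavailable. An end before dosing proves a pre-dose onset. An end after dosing says nothing about onset, yet the second row assigns TEAE on that alone, even where the known part of the start already shows that the event preceded dosing. For these events the class turns on whether an end was recorded.

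Three other rules then use the flag:

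- **24-hour tables (SAP 11.2).** A TEAE with missing start time is placed in the 24-hour window if its start date is no later than one day after the infusion end date. There is no lower bound, so an event dated before dosing would appear among events occurring within 24 hours of dosing.
- **Related TEAEs (SAP 11.2).** Missing causality is set to 'Yes' for TEAEs and left alone for non-TEAEs.
- **Fatal TEAEs.** SAP 10.2 takes the SAE end date as the death date. An event of pre-dose onset that proves fatal after dosing therefore has a recorded end, and becomes a fatal TEAE if its start is incomplete.

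There is also a practical risk: a programmer who follows the table and a validator who follows the sentence would derive different flags.

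**Working it through.** The plan states no figure on this point, so the check is of the rule itself.

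**One event, two end dates.** Take dosing on 15 September at 12:00 and an AE that started on 14 September, time missing.

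| Recorded end | Row reached | Class by the table | Class by the sentence |
|---|---|---|---|
| 18 September | second row, end at or after dosing | TEAE | non-TEAE |
| none | start-date row, time missing | non-TEAE | non-TEAE |

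The onset is the same in both lines. Only the presence of an end differs.

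**All combinations.** I applied the table in its printed order and compared it with the sentence, coded as non-TEAE if either the known start elements or the end shows a pre-dose onset. The grid was:

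- 3 dosing dates (mid-month, first of a month, 1 January)
- 4 missing patterns (time; day; day and month; everything)
- 2 onsets (day before dosing, day of dosing)
- 3 ends (before dosing, three days after dosing, missing)

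That is 3 × 4 × 2 × 3 = 72 cases. The two rules disagree in 6:

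| Missing start element | Discordant cases | Condition |
|---|---|---|
| Time | 3 | start date is the day before dosing; arises at every dosing date |
| Day | 2 | onset falls in an earlier month than dosing |
| Day and month | 1 | onset falls in an earlier year than dosing |
| Everything | 0 | no start element is known |

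In all 6 the end is after dosing, the table gives TEAE and the sentence gives non-TEAE. The six are cells of a constructed grid, not an expected frequency.

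**Cases where the order of rows makes no difference.**

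- Onset on the dosing date with time missing and the end after dosing or missing: TEAE either way, because the start date is not before the dosing date.
- Complete start date and time: the event never enters the table and follows the onset definition.

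**After reordering.** With the start-date checks placed first, the 6 discordant cases become non-TEAE and the other 72 − 6 = 66 do not change.

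**Scale of one event.** The documents give no rate of missing start times, so no count can be derived. If all 62 planned subjects in an arm are dosed, one subject flagged only through such an event adds 1/62 = 1.6 percentage points to the table row concerned. A subject who already has another TEAE in that row adds nothing.

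**The case against.** **The right rule is already stated.** The sentence above the table is correct and the table is meant to implement it, so this is a drafting inconsistency and not a considered analysis choice. That is a fair description. But the table is the operational text, and it gives a different answer.

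**The table may be deliberately worst-case,** as SAP 11.2 is elsewhere. This does not fit. The sentence expressly exempts events whose partial dates show pre-dose onset, and the table's own last row calls the same event non-TEAE when the end is missing. The looser protocol wording does not help either, since being reported after dosing is not the same as ending after dosing.

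**The consequences are small.** This stands. The error only adds TEAEs. Onset precedes double-blind dosing, so no imbalance between arms is expected. SAP 11.2 lists all AEs whatever their start date, so a misplaced event can be seen. SAP 10.3 makes every test but the primary one descriptive.

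**Stronger readings that the documents do not support.** A reader might infer that every AE with pre-dose onset, missing start time and post-dose end is misclassified. It is not: same-day onset with missing time is a TEAE under either order, and Protocol 3 allows screening on Day 1, so such events are a real part of the window. A reader might also infer that the presenting symptoms of COVID-19 would be counted as treatment-emergent. Protocol 10.1.1 sends illness present before study entry to medical history unless it increases in frequency or severity, and Protocol 10.6.1 does the same for a pre-existing condition noticed late. What remains is new or worsened events between consent and dosing.

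**Conclusion.** The inconsistency is real and confined to SAP 11.2: the table contradicts both the sentence that introduces it and the onset-based definition. It affects only AEs with a missing start element whose known part precedes the date, month or year of dosing and which have a recorded end after dosing. With screening limited to 2 days, the realistic case is a start date before the dosing date with no time. The other patterns need a month or year boundary inside that window.

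The effect is a likely small over-count of TEAEs, similar by arm, with knock-on entries in the 24-hour, related and fatal tables. It has no bearing on the primary efficacy result. This is a minor point, worth correcting because the correction is almost free.

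The conclusion assumes that the rows are applied in printed order and that 'otherwise' means that the end rows could not be evaluated.

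**What to change.** Reorder the table for AEs with an incomplete start so that it reads:

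1. Non-TEAE if the known start elements (year; month and year; or date) precede those of IP.
2. Non-TEAE if the AE end is before IP start.
3. Otherwise TEAE.

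This puts the SAP's own sentence into effect and keeps TEAE as the default. Events corrected in this way also drop out of the 24-hour, related and fatal TEAE tables, so those rules need no separate change for this purpose. The cost is one edited table in the SAP and the matching line in the programming specification, with no change to data collection. It should be made before unblinding.

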10.1.3 Adverse Event of Special Interest

There are several AEs that will be monitored closely as AESIs to enable an adequate risk-benefit evaluation of CSL312 during the study and additional data may be requested for these events. The AESIs will be:

- Bleeding events that are abnormal in the opinion of the investigator
- TEEs
 - Non-systemic thrombosis (eg, localized thrombosis associated with vascular access) is not considered an AESI
- Severe hypersensitivity including anaphylaxis

The reporting requirements for AESIs are detailed in [Section 10.6.1](#).

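### The SAP requires the AESI flag to match an SMQ-based definition that omits the three limits in the protocol's AESI definition, and declares no change

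*SAP*

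**What the plan says.** Protocol 10.1.3 names three AESI categories, and each has a limit:

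- Bleeding: "Bleeding events that are abnormal in the opinion of the investigator".
- Thromboembolic events, with a carve-out: "Non-systemic thrombosis (eg, localized thrombosis associated with vascular access) is not considered an AESI".
- Hypersensitivity: "Severe hypersensitivity including anaphylaxis".

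Table 3 in protocol 7.3 repeats the words abnormal (for bleeding) and severe (for hypersensitivity). Protocol 2.2.2 and SAP Table 1 both list AESIs among the secondary safety endpoints, summarised as the number and proportion of subjects affected.

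SAP 11.2 makes two statements in sequence. The first follows the protocol: "AEs fulfilling the definition of an AESI for this study will be ticked in the AE CRF". The second sets a cleaning rule: "It will be ensured during data cleaning that the AESI recording on the AE CRF matches the AESI definition obtained by Standardized MedDRA Queries". Four SMQs follow: Hypersensitivity (broad), Anaphylactic reaction (broad), Embolic and thrombotic events, and Haemorrhages. The last two have no scope.

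SAP Section 5 states: "There are no changes to the analyses planned as specified in the study protocol".

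**The concern.** The two statements in SAP 11.2 rest on different definitions. The first sends the site to the protocol. The second makes the SMQ result the standard and the CRF record the thing that has to agree with it. No rule says what happens when the two disagree for a good reason, for example a bleed whose term is in the SMQ but which the investigator did not find abnormal.

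What is at stake is the meaning of a named secondary safety endpoint. Protocol 1.4 identifies bleeding, thromboembolism and severe hypersensitivity as potential risks of the product, and the AESI count is the summary designed for them. If the flag is aligned to the SMQs, the reported count answers a different question from the one in the protocol, and Section 5 does not tell the reader.

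**Working it through.** No AESI figure is stated in either document, so there is nothing to reproduce. The check sets the two texts side by side.

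| Category | Limit in protocol 10.1.3 | SAP 11.2 standard | Is the limit carried over? |
|---|---|---|---|
| Hypersensitivity | Must be severe; anaphylaxis included | Hypersensitivity SMQ, broad; Anaphylactic reaction SMQ, broad | No severity condition |
| Bleeding | Investigator must judge it abnormal | Haemorrhages SMQ, scope not stated | No investigator judgement |
| Thromboembolic events | Non-systemic thrombosis excluded | Embolic and thrombotic events SMQ, scope not stated | No exclusion |

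All three limits are missing. The SAP heading for the hypersensitivity listing also leaves out the word severe.

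**Can an SMQ match reproduce the protocol definition?** Let P be the events meeting protocol 10.1.3, and S the events whose coded term falls in one of the four SMQs. The protocol endpoint counts subjects with at least one event in P. If the CRF flag is made to match the SMQs, the endpoint counts subjects with at least one event in S. Then

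count under S − count under P = (subjects with an event in S but none in P) − (subjects with an event in P but none in S).

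- *Events in S but not P.* Membership of S depends on the coded term. Membership of P also depends on severity and on the investigator's judgement. SAP 11.2 itself tabulates events by preferred term and intensity, so one term can occur at several intensities. A term list therefore cannot apply the severity limit, and still less an opinion on abnormality. For thrombosis, a term might indicate the site, but the SAP removes no terms from the SMQ.
- *Events in P but not S.* An event that the investigator ticked correctly under the protocol, but whose coded term lies outside the SMQs, would fail the match.

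The count can therefore move in either direction. Neither bracket can be evaluated from the documents.

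**Do the other planned outputs restore the protocol count?** Only in part. SAP 11.2 plans all treatment-emergent events by preferred term and intensity, AESIs by System Organ Class and preferred term, and by-subject listings for each AESI group. Severity could be recovered from these. No planned table shows whether a bleed was judged abnormal or whether a thrombosis was systemic. The CRF tick carries those two decisions, and it is the tick that has to match.

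**Does the version gap explain the difference?** No. SAP Section 3 bases the SAP on protocol Amendment 2. The Amendment 3 entry in the revision history lists only the duration of contraception and a thermometer method.

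**The case against.** The strongest reply is that the study definition still drives the tick and the SMQ sentence is only a completeness check. The SAP describes no procedure for changing ticks, and comparing flags with SMQs is a sensible way to find omissions. That may well be the intention. But the sentence promises a match, not a query, and leaves no room for a valid disagreement. If a query process is meant, the text has to say so.

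A second reply is that Section 5 concerns planned analyses, and those are unchanged: protocol 11.5 plans counts and percentages, and SAP 11.2 delivers them. This is right about the summary measure. What differs is which events enter it, and a reader of Section 5 would not expect that.

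A third reply is that little depends on the count. This stands. SAP 10.3 allows one confirmatory test and calls the rest descriptive, no AESI test is specified, and the primary analysis is untouched. The monitoring committee reviews accumulating unblinded data (protocol 8.1), and the halting criteria (protocol 8.2) do not use AESI totals.

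Several stronger readings are tempting, but the documents do not support them:

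- A reader might infer that the SAP overwrites investigators' decisions with broad definitions. Broad is stated for two SMQs of four, and no mechanism of change is described.
- A reader might infer that mild rashes, trivial bleeds and catheter thromboses will become AESIs. The SMQ contents are not in the documents; such events could be counted if their terms are included.
- A reader might infer that the extra events would hide a bleeding or thrombosis signal. No rates are given, and the term-level tables and listings remain.
- A reader might infer that re-ticking triggers expedited reporting. Protocol 10.6.3 attaches that duty to AESIs, which protocol 10.1.3 defines, and neither document says that a cleaning-stage match changes it.

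**Conclusion.** The inconsistency is real and should be corrected. SAP 11.2, as written, makes an SMQ-based definition the standard for the AESI flag, and that definition lacks every limit set in protocol 10.1.3. Followed literally, it yields an AESI endpoint other than the one the protocol defines, with no change declared.

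The effect is confined to a descriptive safety summary. Its size and direction cannot be derived: it is zero if the flagged and retrieved events happen to coincide, and otherwise depends on SMQ contents and event rates that the documents do not give. The conclusion rests on reading the cleaning sentence as a requirement to match. If the sponsor intended only a check for missed events, the remedy is a change of wording and the endpoint is unaffected.

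**What to change.** Amend SAP 11.2 as follows:

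1. Define the AESI endpoint as events that the investigator flags on the AE CRF under protocol 10.1.3, with its severity condition, judgement of abnormality and exclusion of non-systemic thrombosis.
2. Use SMQ retrieval during cleaning only to query possible omissions, and state that the investigator's answer stands.
3. Add a separately labelled supportive table of SMQ-retrieved events by treatment, with the scope stated for all four SMQs.
4. Restore the word severe in the heading of the hypersensitivity listing.

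If the sponsor wants the SMQ definition as the endpoint, SAP Section 5 should declare and justify it as a departure from the protocol.

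The cost is SAP wording and one extra table.
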